10.4.2 STATISTICAL METHODS FOR SECONDARY OUTCOMES

10.4.2.1 CONTINUOUS OUTCOMES

Continuous secondary outcomes will be analysed similarly to the primary outcome

10.4.2.2 BINARY OUTCOMES

Logistic regression will be used to analyse secondary binary outcomes.

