10.3 SAMPLE SIZE JUSTIFICATION

To detect an effect size of 0.4,^{85,86} with 90% power and 5% significance (2-sided), a sample of 266 is required for an individually randomised trial. To inflate to a cluster RCT design, by randomising 26 PDU/JSWT with an average cluster size of 13.5 and an ICC=0.03,⁸⁷ the number analysed is inflated to 358. To account for 18% drop out of both offenders³⁷ and PDU/ JSWT we will plan to randomise 32 PDU/ JSWT (1:1) and enrol 450 offenders (14 per PDU/ JSWT).

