potentially a billion comparisons that could be made. The blocking rules allow for most of this potential billion to be ignored.

Conducting the probabilistic linkage involves calculating 3 fundamental statistics.

- The m-probability is the likelihood that 2 records match on a given field, if the records are a true match (the records belong to the same person).
- The u-probability is the likelihood that 2 records match on a given field, if the records are a false match (the records belong to different people).
- Lamda is the overall probability that any 2 randomly selected records are a match. We can then apply Bayes' formula to assign a single probability that each pair of records is related to the same individual across the 2 systems.

Splink is a Python package designed to implement the Fellegi-Sunter algorithm at scale. This is implemented on a secure partition of UKHSA's network (where NDTMS is also stored) with limited personnel access.

Other data linkage will be conducted using participants full name.

PROCESS EVALUATION: Context, fidelity, dose delivered, dose received, reach and recruitment for ADVANCE-D will be evaluated. 88 Longitudinal qualitative interviews (at 4- and 12- months) with 40 men receiving ADVANCE-D and their (ex)-partners and with staff post intervention will provide in-depth understanding of mechanisms of action, how context affects implementation, engagement, and behaviour change.

ANALYSIS OF RECORD LINKAGE: A long term follow-up will be carried out at 24-month via record linkage. This analysis will be described in the SAP and assess recidivism (criminal justice data), mortality (via Office for National Statistics), drug treatment (via NDTMS/SMR), prescription (NHS Digital/Public Health Scotland) and hospital admission data (via HES/SMR). Mortality will be analysed with a multi-level logistic regression in a similar manner to the primary outcome.

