ECONOMIC EVALUATION: A senior health economist will oversee the analysis conducted by the trial health economist. An economic evaluation will be embedded within the study to compare ADVANCE-D with usual CJOM. The costs of providing ADVANCE-D and usual CJOM will be recorded prospectively and include the cost of staff time, training, overheads and consumables. We will first use clusters as the costing unit to calculate an intervention delivery cost per cluster. Once the treatment ends, we will assign the cluster costs proportionally to each participant according to their attendance. This will result in an intervention delivery cost per participant and reflect variance among participants. Quantities of resources used will be collected alongside the study and local unit costs will be applied to derive the cost per participant in treatment condition. This will provide a costing of the interventions with a per patient cost attached. Health care utilisation data for contacts with NHS primary care, secondary care, personal social services (PSS), will be collected using a SUQ by self-report at each follow up. The published secondary sources of unit costs of these services of the appropriate year⁸⁹⁻⁹¹ will be applied to the quantities up to form the costs from the NHS/PSS perspective⁹². We will collect resource use outside of the NHS/PSS domain (criminal justice contacts, legal aid, housing service, productivity losses) using the SUQ via self-report, and apply national average costs to these quantities to derive patient cost outside of the NHS/PSS perspective. Incidents of IPV will be collected in the SUQ. The aggregate costs in each category will be presented as part of the cost-consequences analysis. Secondary care contacts are taken from the record linkage with HES. Quantities recorded are multiplied by national average unit costs for health care and criminal justice contacts to derive cost profiles for all participants. Study participants will also complete EQ-5D-5L at baseline and each follow up and we will calculate QALYs using the area under the curve. 91 We will use the tariff as recommended by NICE at the time of analysis to derive health related quality of life (HRQoL) utility scores from the EQ-5D-5L data. 92 Participant costs (intervention and NHS/PSS costs) 89.90 are combined with QALYs to estimate the incremental cost per QALY of the intervention over and above CJOM at follow up. Underlying uncertainty around the decision to adopt the intervention is assessed using non-parametric bootstrap re-sampling. Bootstrapping is an efficient method for calculating the confidence limits for the incremental cost effectiveness ratio (ICER) as its validity does not depend on any specific form of underlying distribution. We perform 5000 replications and construct the 95% CI for the ICERs based on the

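### The stated rules for binary secondary outcomes and for cost-effectiveness uncertainty do not carry the PDU/JSWT clustering that the protocol's other models carry

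*Protocol*

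**What the plan says.** The protocol treats clustering differently from one analysis to the next.

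- **Primary outcome (10.4.1).** Multi-level linear regression, with participants and PDU/JSWT as random effects and the ICC reported.
- **Continuous secondary outcomes (10.4.2.1).** Handled by reference to the primary model, so they inherit the cluster effect.
- **Binary secondary outcomes (10.4.2.2).** The whole rule is: "Logistic regression will be used to analyse secondary binary outcomes". It has no cluster term and no reference back to the primary model.
- **24-month mortality (10.7, analysis of record linkage).** "Mortality will be analysed with a multi-level logistic regression in a similar manner to the primary outcome".
- **Cost-effectiveness (10.7, economic evaluation).** "Underlying uncertainty around the decision to adopt the intervention is assessed using non-parametric bootstrap re-sampling". The section fixes 5000 replications, a 95% interval for the ICER and acceptability curves. It justifies the bootstrap by its freedom from a distributional form. It does not name the resampling unit, and it gives no multi-level model for costs or QALYs.

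The sample size (10.3) allows for clustering: "by randomising 26 PDU/JSWT with an average cluster size of 13.5 and an ICC=0.03".

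**The concern.** When clusters are randomised, men in the same PDU/JSWT are not independent observations. A logistic model without a cluster term, or a bootstrap that resamples individual men, treats them as if they were. Standard errors then come out too small whenever the ICC is above zero.

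The justification given for the bootstrap deals with the shape of the distribution. It does not deal with independence of the resampled units, which is what cluster randomisation takes away.

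The contrast inside the protocol makes this more than brevity. The authors use multi-level wording for one binary outcome (mortality) and a link to the primary model for continuous outcomes, but 10.4.2.2 has neither. Adherence and compliance are expressly left to the SAP, while 10.4.2.2 states a method and defers nothing.

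At stake is how certain any binary secondary result, the ICER interval and the acceptability curve would appear to be.

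**Working it through.** **Inputs, all from Protocol 10.3.** "To detect an effect size of 0.4"; "with 90% power and 5% significance (2-sided), a sample of 266 is required for an individually randomised trial"; 26 clusters with an average of 13.5 men and ICC 0.03; "the number analysed is inflated to 358"; "To account for 18% drop out of both offenders"; 32 clusters and 450 men enrolled.

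**Step 1: the plan's own figures.**
- Individually randomised: a two-sample t calculation for a standardised difference of 0.4 gives 266, as stated (the normal approximation gives 264).
- Design effect: DE = 1 + (m − 1) × ICC = 1 + 12.5 × 0.03 = 1.375.
- Clustered: 266 × 1.375 = 365.75, so 366 against the stated 358, about 2% apart.
- Dropout: 366/0.82 is about 447 and 358/0.82 about 437, against 450. Clusters: 26/0.82 = 31.7, so 32.

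The figures reproduce closely enough to show that the protocol itself works with a design effect near 1.375.

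**Step 2: the effect of leaving the cluster out.** The true standard error exceeds the reported one by √DE. The real two-sided error of a nominal 5% test is 2 × (1 − Φ(1.96/√DE)), and a 95% interval is too narrow by 1 − 1/√DE.

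| ICC | m | DE | SE factor | Interval too narrow by | Real type I error |
|---|---|---|---|---|---|
| 0.01 (assumed) | 13.5 | 1.125 | 1.06 | 5.7% | 6.5% |
| 0.03 (from 10.3) | 13.5 | 1.375 | 1.17 | 14.7% | 9.5% |
| 0.05 (assumed) | 13.5 | 1.625 | 1.27 | 21.6% | 12.4% |

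At ICC 0.03 and m = 13.5, real coverage of a 95% interval is about 90.5%.

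**Step 3: smaller clusters at ICC 0.03.**
- Men, if all 32 clusters stay and 18% of men drop out: m = 450 × 0.82/32 = 11.5, DE 1.32, error about 8.7%.
- Women, if the earlier studies' rates in 3.7.1 recur. Recruitment was 26% and 47%, and 4-month follow-up of those recruited was 63% and 52%. That gives 14 × 0.26 × 0.63 = 2.3 and 14 × 0.47 × 0.52 = 3.4 women per cluster, DE 1.04 to 1.07, and error about 5.4% to 5.8%.

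**Step 4: simulation check at ICC 0.03, 26 clusters of 13 or 14.**
- Binary data with event rates of 20% and 40%, 20,000 runs each: logistic analysis without clusters rejected a true null in 8.9% to 9.5% of runs. A cluster-level analysis rejected in 4.7% to 5.1%.
- Bootstrap of a mean difference, 2,000 runs: true SE 0.124, resampling men 0.106, resampling clusters 0.119. The ratio 0.124/0.106 = 1.17 matches Step 2.

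**The case against.** The strongest reply is that this is silence, not error. The text does not say that the logistic regression is unclustered, and a bootstrap that resamples clusters is also non-parametric. A reader might infer that the protocol prescribes ordinary logistic regression and a participant-level bootstrap, so that the intervals will certainly be too narrow. The documents do not support that: neither rule excludes a cluster effect, robust standard errors or cluster resampling, and the SAP, which is not shown, may supply them. What remains is that the rules as written omit the clustering where parallel rules include it.

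Reach is also limited. Section 10.2 lists mainly scale scores and counts of days and designates none as binary. The cut-offs in 3.7.4 for PHQ-9, GAD-7 and PC-PTSD-5 describe the instruments and do not declare dichotomised endpoints. The economic objective in 2.2 is a cost-consequences analysis, with the ICER and acceptability curve reported in addition. All of this stands.

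The size is conditional too, because 0.03 is a sample-size input and no ICC is given for binary outcomes, costs or QALYs. This can cut the other way: 10.7 builds the delivery cost per cluster and shares it among that cluster's men by attendance, so the ICC for costs could exceed 0.03.

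Two further criticisms are tempting: that the multiple imputation names no cluster term, and that the binary rule does not say how the 4- and 12-month assessments are combined. Neither is supported. The protocol lists no imputation variables at all, separate models at each time point would be legitimate, and such detail normally belongs in the SAP.

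**Conclusion.** The point holds as an internal inconsistency of moderate severity. The binary-outcome rule and the bootstrap rule do not carry the PDU/JSWT clustering, unlike the primary, continuous secondary and mortality analyses. Read literally, and assuming ICC 0.03 with 13.5 men per cluster, standard errors would be too small by a factor of about 1.17 and a nominal 5% test would run at about 9.5%. Over assumed ICCs of 0.01 to 0.05 the range is 6.5% to 12.4%, and partner outcomes would be barely affected.

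The primary result and 24-month mortality are untouched. Since no listed secondary outcome is designated binary, the practical weight falls on the ICER interval and the acceptability curve. A reader might infer that the trial's main conclusion is at risk or that the protocol cannot stand until this is changed. Neither follows, because the primary model already includes the cluster.

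**What to change.** - **10.4.2.2:** specify multi-level logistic regression with a PDU/JSWT random effect, aligned with the primary model as is already done for mortality.
- **10.7, economic evaluation:** state that the bootstrap resamples PDU/JSWT within arm (a cluster or two-stage bootstrap), or use a multi-level cost-QALY model.

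The cost is a sentence in each section and minor programming, with no new data. Intervals become slightly wider. If the SAP or a health economics plan already says this, the protocol wording only needs to be brought into line.

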10.4.3 ADHERENCE

To be defined in the Statistical Analysis Plan.

10.5 Interim analyses (statistical)

No formal interim analyses.

10.6 INTERNAL PILOT

INTERNAL PILOT: 168 participants from 12 clusters will be randomised in the internal pilot.

PROGRESSION CRITERIA: A year after randomising the first PDU/JSWT, we will assess the feasibility of the trial with the following progression criteria: 12 PDU/JSWT randomised (>9 modifications needed, \leq 8 stop trial); letters of support received from the remaining 24 PDU/JSWT (>19 modifications needed, \leq 18 stop trial); 168 participants enrolled (>123 modifications needed, \leq 122 stop trial); 80% followed-up at 4

months and 80% intervention adherence (>65% modifications needed, ≤ 64% stop trial). If all criteria are met, we will ask the Trial Steering Committee (TSC) to recommend progression to the trial.

Progression Criteria	Go	Revise strategy	Stop Trial
PDU/ JSWT randomised	≥12	9 to 11	≤ 8
PDU/ JSWT letters of support	≥ 24	19 to 23	≤ 18
Offenders enrolled	≥168	123 to 167	≤ 122
Adherence to the programme by offenders	≥ 80%	65 to 79%	≤ 64%
Follow up of offenders	≥ 80%	65 to 79%	≤ 64%

STOPPING CRITERIA: The trial may be prematurely discontinued by the Sponsor or CI on the basis of new safety information (e.g. that the ADVANCE-D Programme caused harm or greater risk) or for other reasons given by the Data Monitoring Committee (DMC) regulatory authority or ethics committee concerned. The trial may also be prematurely discontinued due to lack of recruitment or upon advice from the Trial Steering Committee (TSC), who will advise on whether to continue or discontinue the study and make a recommendation to the sponsor. If the study is prematurely discontinued, active participants will be informed, and no further participant data will be collected.

The DMC will provide advice to the TSC, who will advise the Sponsor in making the final decision on continuing or stopping the trial.

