3. PARTICIPANTS

3.1 STUDY SETTING & RECRUITMENT

Courts mandate sentences to men convicted of IPV. Sentences include a rehabilitation activity requirement (RAR) in England; or a community payback order (CPO) in Scotland. These requirements/orders are given with a view to promoting the offender's rehabilitation and reduce the likelihood of reoffending. Men must see a Probation Practitioner (PP) at a Probation Delivery Unit (PDU; England)/ Justice Social Worker (JSW) at a Justice Social Work team (JSWT; Scotland) within 5 days post sentencing when sentence planning will take place. PDU/ JSW team make decisions on the offender management required to address any support recommended by court. Alongside the RAR or CPO, men will have a supervising PP/ JSW to monitor compliance to the community sentences. Any violation of conditions will be referred back to court.

There are 11 probation regions in England. PDU are the local units in each of these probation regions. For example, Greater Manchester (probation region) has 9 local PDU (see Table 1). Scotland has 32 Justice Social Work areas (JSW area) that provide statutory criminal justice services in JSWT. For example, City of Edinburgh (JSW area) has 2 local JSW teams (see Table 1). PDU and JSWT will be treated as clusters for the purpose of the trial.

To be eligible to take part in the trial, PDU and JSWT must have a central intervention delivery model (e.g. a central intervention delivery team in Greater Manchester deliver interventions across all 9 PDU); have trained and certified facilitators and partner support workers; and not be sites in other intervention trials. Facilitators in each Probation Region (England) and JSW area (Scotland) will be trained to centrally deliver the ADVANCE-D Programme and will be blind to allocation of PDU/ JSWT. Each PDU/ JSWT will recruit and consent 14 men to the trial before the outcome of allocation is known to them.

A total of 32 PDU/ JSWT are required for the cRCT. Twelve PDU/ JSWT (clusters) from the 24 clusters in Table 1 will be allocated at random for men to receive the ADVANCE-D Programme delivered by a central team + usual community justice offender management (CJOM) (Option 1) OR usual CJOM (Option 2) during the internal pilot from two probation regions from England (Greater Manchester and the North West) and one JSWT from Scotland (City of Edinburgh). An additional 20 PDU/ JSWT will be recruited to the main trial.

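### The letters-of-support progression criterion is set on 24 remaining clusters, but the protocol's own design leaves 20

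*Protocol*

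**What the plan says.** Section 3.1 gives the cluster count and its split: "A total of 32 PDU/ JSWT are required for the cRCT", and, after the pilot, "An additional 20 PDU/ JSWT will be recruited to the main trial". The synopsis, section 2 and section 10.3 also give 32. Section 10.6 gives the pilot size: "168 participants from 12 clusters will be randomised in the internal pilot".

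The progression criteria in section 10.6 then require "letters of support received from the remaining 24 PDU/JSWT". The table row headed "PDU/ JSWT letters of support" sets Go at 24 or more, Revise at 19 to 23 and Stop at 18 or fewer. The TSC is asked to recommend progression if all criteria are met.

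The same section states the cut-offs twice. The running text opens the middle band strictly above a value, for example "12 PDU/JSWT randomised (>9 modifications needed" for clusters and ">19 modifications needed" for letters, and likewise above 123 men and above 65%. The table opens it at 9, 19, 123 and 65%.

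**The concern.** The word remaining ties the 24 to the clusters left after the pilot, and that number is 20 everywhere else in the protocol. The three limits in the row follow from the 24, so the error carries into the thresholds and not only into the description.

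These limits were fixed in advance so that the decision to continue would not be shaped by the pilot results. If they are wrong, a pilot that secured every cluster the trial still needs would miss Go on this row, and one that secured nine in ten would be graded as a reason to stop. The committee would then have to set aside or reinterpret a pre-specified rule after seeing the data.

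**Working it through.** **The total of 32.** Section 10.3 uses 26 clusters before attrition and 18% drop-out: 26 / (1 − 0.18) = 31.7, which rounds up to 32. The stated total reproduces.

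**The pilot.** 12 clusters × 14 men = 168, as section 10.6 states.

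**Clusters left.** 32 − 12 = 20, which agrees with section 3.1. The progression rule implies 12 + 24 = 36 clusters, a total that appears nowhere in the protocol.

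**A possible source of the 24.** Section 3.1 says "Twelve PDU/ JSWT (clusters) from the 24 clusters in Table 1 will be allocated at random". The pilot clusters are drawn from those 24, so at most 24 − 12 = 12 of that list remain. The list does not yield 24 remaining clusters.

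**The rule applied to the letters received.**

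| Letters | Share of 20 | Table | Text |
|---|---|---|---|
| 18 | 90% | Stop | Stop |
| 19 | 95% | Revise | in no band |
| 20 | 100% | Revise | modifications needed |
| 21 to 23 | more than 20 clusters | Revise | modifications needed |
| 24 | more than 20 clusters | Go | Go |

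Go lies four letters above the number of clusters that remain.

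**What Stop at 18 would mean.** With 18 letters the trial would have 12 + 18 = 30 of its 32 clusters in prospect. On the inputs of section 10.3 (effect size 0.4, ICC 0.03, 14 men per cluster, 18% loss), the number analysed is 30 × 14 × 0.82 = 344. Power is approximately Φ(0.4 × √(n_eff) / 2 − 1.96), where n_eff = 344.4 / design effect:

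- Loss of whole clusters: design effect 1 + (14 − 1) × 0.03 = 1.39, n_eff = 248, power about 88%.
- Loss of men within clusters: mean size 14 × 0.82 = 11.48, design effect 1 + 10.48 × 0.03 = 1.314, n_eff = 262, power about 90%.

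The Stop limit would therefore be met with power close to the planned 90% still in prospect. This is a normal approximation and assumes that every cluster with a letter goes on to recruit.

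**The other count rows for comparison.** Stop is at 8/12 = 67% for clusters randomised and 122/168 = 73% for men enrolled. Against 20 clusters, the letters row stops at 90%.

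**The row's own proportions carried to 20.** 18/24 = 75%, and 75% of 20 is 15. 19/24 = 79%, and 20 × 19/24 = 15.8, so 16. The equivalent limits are Go at 20, Revise at 16 to 19 and Stop at 15 or fewer.

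**Text against table.** At exactly 9 clusters, 19 letters, 123 men or 65%, the table says Revise. In the text the value is neither above the modification cut-off nor at or below the stop cut-off (8, 18, 122, 64%), so it has no grade. Go and Stop limits agree between the two for every criterion.

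**The case against.** A letter of support expresses willingness and is not a randomised place, so a team could sensibly seek more letters than it has places. The table row gives no denominator, and section 3.1 describes a pool larger than 32 clusters: 11 English probation regions, each made up of local units, and 32 Scottish justice social work areas. On that reading 24 letters for 20 places could be obtained. This stands to the extent that a reader might infer from the arithmetic that Go is impossible, and the protocol does not establish that. But it names no reserve, the word remaining points the other way, and a Stop limit of 18 would still apply with 90% of the places covered.

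A reader might also infer that 18 letters would close the trial. Section 10.6 does not say so: the TSC advises and the Sponsor decides, so an oversight body could recognise that 18 of 20 is no reason to stop. That limits the harm but leaves the threshold wrong as written.

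The boundary mismatch is small. It concerns one value per criterion, the table resolves it, and no Stop grade changes.

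Two further criticisms of the same criteria are tempting, and the document does not support them:

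- The 80% follow-up target might look too low beside the 18% drop-out in section 10.3. But 358 to be analysed out of 450 enrolled is 79.6%, and 80% of 450 is 360, so the target matches the number needed. The 18% also covers loss of clusters.
- The percentage bands might look as if they leave gaps between 64 and 65 and between 79 and 80. They are contiguous in whole percentages, the unit the table uses.

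**Conclusion.** The inconsistency is real. The letters criterion rests on 24 remaining clusters where the design leaves 20. With no letters sought outside the 32 clusters, 20 of 20 grades as Revise and 18 of 20 as Stop; with at least four reserve clusters approached, Go becomes reachable but the Stop limit remains out of line with 20 places. The conclusion rests only on the stated counts of 32, 12 and 20.

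It should be corrected before the pilot review because it is a pre-specified threshold bearing on whether the trial continues. It has no bearing on the sample size, the type I error or the primary estimate. The difference between text and table is a minor companion point.

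**What to change.** Amend section 10.6, agreed with the TSC, before the pilot review. Choose one of two routes for the letters row:

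1. Rebase it on the 20 remaining clusters. For illustration, the row's own proportions give Go at 20, Revise at 16 to 19 and Stop at 15 or fewer. Other limits are defensible, since the other rows use different proportions.
2. If a reserve was intended, state that 24 letters are sought for 20 places, say where the additional clusters come from, and reset the Stop limit to fit 20 places.

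In the same amendment, change the text cut-offs to at least 9, 19, 123 and 65%, so that they match the table.

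The cost is a protocol wording change and the TSC's agreement. It has no operational cost.

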A researcher will then text or call the consented participant and complete the baseline interview with the participant in person at the PDU/JSWT or by phone or video call. All men from a cluster should be baselined within two weeks. This call will not be undertaken in the presence of a PP/ JSW. During this call, researchers will check the participant still wishes to take part in the trial, that they have consented to take part in the trial of their own free will and are fully informed of what taking part in the study involves. Participants will have the opportunity to opt out of the trial at this point without any repercussions to their CJOM. This timeframe allows the participant up to two weeks from consenting to take part to decide whether they still wish to take part.

A researcher will be responsible for completing a baseline interview with consented men by phone, video conferencing, or in person at the PDU/JSWT. This will not be conducted in the presence of a PP/JSWT. Interviews will never be conducted in participants' homes.

Only after the men are consented and baselined in each PDU /JSWT and their female current or expartners have been consented and baselined; will participants and PDU/ JSWT team be told what treatment arm they have been allocated to.

For current or ex-partners

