5.3.2 ENROLMENT OF PARTICIPANTS

Participants will be enrolled in the study for the purpose of $CONSORT^{84}$ reporting at the point of signing a consent form and will be part of the target N=450 at the point of randomisation.

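### The pilot progression rule counts men enrolled, which the protocol defines as consented, while the pilot's stated size is men randomised

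*Protocol*

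**What the plan says.** Section 10.6 of the protocol opens by sizing the pilot: "168 participants from 12 clusters will be randomised in the internal pilot". The progression criteria that follow count something else. The text has "168 participants enrolled (>123 modifications needed", and the table row is "Offenders enrolled ≥168 123 to 167 ≤ 122". A separate row counts clusters: "PDU/ JSWT randomised ≥12 9 to 11 ≤ 8".

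Section 5.3.2 distinguishes the two counting points. A man is enrolled for CONSORT "reporting at the point of signing a consent form and will be part of the target N=450 at the point of randomisation".

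The steps between those points are set out elsewhere:

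- Section 3.1: "Each PDU/ JSWT will recruit and consent 14 men to the trial before the outcome of allocation is known to them".
- Section 3.4.4 describes 14 as an approximate figure, settled site by site according to recruitment.
- Section 3.4.5 has a researcher contact each consented man, confirm that he is still willing, and then carry out the baseline interview.
- Section 3.3, on that contact: "Participants will have the opportunity to opt out of the trial at this point without any repercussions to their CJOM".
- Section 5.2 assigns clusters only after baseline data have been collected.
- Section 5.3.3 closes recruitment at a site when an adequate number of men have both consented and completed baseline.

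**The concern.** A progression rule should be stated in the same unit as the target it tests. Here the target is in men randomised and the rule is in men enrolled, and the protocol's only definition places enrolment at an earlier step. Any man lost between the two still counts towards Go.

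What is at stake is a Go/Revise/Stop decision put to the Trial Steering Committee. The proportion of consented men who reach baseline and randomisation is also something an internal pilot is well placed to measure, and this criterion does not measure it.

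**Working it through.** **Reproducing the plan's figure.** Inputs: 12 pilot clusters (10.6) and 14 men per cluster (3.1, 3.4.4, 10.3). 12 × 14 = 168, which matches exactly. In 3.1 and 3.4.4 the 14 is a number of men consented, so the product contains no allowance for men lost before randomisation.

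**Smallest possible discrepancy.** Using the table's bands (Go ≥168, Revise 123 to 167, Stop ≤122):

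- 168 consents less one man lost = 167 randomised. The rule reads Go; the randomised count lies in Revise.
- 123 consents less one man lost = 122 randomised. The rule reads Revise; the randomised count lies in Stop.

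**Size under assumed losses.** The documents give no rate of loss *d* between consent and randomisation, so the values below are assumptions. If exactly 168 men consent, the number randomised is 168 × (1 − *d*), and the consents needed to randomise 168 are 168 / (1 − *d*), rounded up.

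| Assumed *d* | Randomised from 168 consents | Band on that count | Consents needed for 168 |
|---|---|---|---|
| 0% | 168 | Go | 168 |
| 5% | 159.6 (about 160) | Revise | 177 |
| 10% | 151.2 (about 151) | Revise | 187 |
| 20% | 134.4 (about 134) | Revise | 210 |

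For 168 consents to correspond to Stop, at least 168 − 122 = 46 men would have to be lost, and 46 / 168 = 27.4%. With exactly 168 consents, a Go that should have been a Stop therefore needs a loss of about 27% or more. A Go that should have been a Revise needs the loss of only one man.

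**Whether another criterion closes the gap.** The cluster row counts units, so a cluster with few baselined men scores the same as a full one. Letters of support do not count men. The follow-up and adherence rows are percentages, and section 10.6 does not state the denominator for follow-up. No row counts men randomised.

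**The case against.** The strongest reply is that the authors meant randomised. Section 5.3.2 defines enrolment for CONSORT, not for progression. Section 10.3 speaks of enrolling 450 men, the same 450 that section 5.3.2 counts at randomisation, so the verb is already used loosely in the statistical section. Section 10.6 gives 168 as a randomised number just before using 168 as the threshold. Men are also registered into the study at the baseline interview (Table 3, section 3.4.5), so the registration count is already of men who reached baseline. This is a plausible account of the intention. It makes the rule ambiguous instead of plainly wrong, but a go/stop threshold should not need that inference.

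It is also fair that Go requires every criterion to be met, that the Trial Steering Committee makes the recommendation, and that a CONSORT flow from consent to randomisation would show the loss. The loss would be visible in reporting; it is simply not what the criterion scores.

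A reader might go further and infer that recruitment is fixed on consents, so that any loss leaves the pilot short of 168 and the main trial short of 450. The documents do not support this. Section 3.4.4 makes 14 an estimate that sites may vary, section 5.3.3 closes recruitment on men who have consented and been baselined, and section 5.3.2 already counts the 450 at randomisation. The wording of the pilot criterion changes none of these, so no main-trial shortfall or loss of power follows from it.

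**Conclusion.** The point holds as a wrongly specified unit in a decision threshold, and it is minor. Read with the protocol's own definition, section 10.6 can return Go when fewer men have been randomised than the pilot is stated to contain. The direction is certain: the consent count can equal or exceed the randomised count, never fall below it. The size is unknown. The figures of about 160 and 151 rest on assumed losses of 5% and 10% and on exactly 168 consents; more consents would reduce or remove the discrepancy. If the authors meant randomised, the correction only makes the rule say so.

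**What to change.** In section 10.6, in both the text and the table, replace *enrolled* with *consented, baselined and in a randomised cluster*. Keep the cut-offs at 168, 123 to 167, and 122. Report the number of men consented as a separate figure, so that the committee sees the conversion from consent to randomisation.

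In section 3.1, align the statement about 14 men with section 5.3.3, so that the cluster figure refers to men consented and baselined.

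The cost is a protocol wording change with no new data collection. The progress figure put to the committee may look slightly less favourable than a count of consents.
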